Recruitment and Enrollment. Potential participants will be recruited by IRB-approved advertisements, as well as referral from current participants. Once initial screening is completed (either over the phone or via the internet), potentially eligible participants will earn \$10 to come to the lab for in-person informed consent, screening, and familiarization with study procedures (approximately 1.5 hrs). Prior to in-person data collection, staff will review the informed consent with potential participants to ensure they understand the study, its risks and benefits, and their rights as research participants. Following documentation of informed consent, participants will complete baseline measures to confirm eligibility and provide a urine sample that will be tested for cotinine level (to confirm current smoking status) and pregnancy (women only). Age will be verified by asking participants to provide some form of identification that includes a date of birth. We will also take pictures of their device/liquid. All study procedures will be reviewed and participants will be asked to choose the ECIG liquid flavor to be used during the four study ECIG sessions (i.e., not their own brand session). They will be given the opportunity to test four ECIG liquid flavors using the study ECIG device (tobacco, menthol, dessert, fruit) during screening. After flavor testing, participants will complete the Balloon Analogue Risk Task (BART) and the Minute Discounting Task (counter-balanced administration). Depending upon task performance, participants will receive up to \$40 in compensation for the actual amount earned at the end of the BART task.

New recruits will replace participants who do not complete the study. Accrual ends when the required number of completers (N=120) is reached.

Products. Own brand tobacco cigarette packs or ECIG liquids consistent with participant preference will be purchased locally following enrollment. For all other sessions we will provide ECIG liquid at 10mg or 30 mg nicotine and an "open system" ECIG (i.e., Kanger Sub Box Mini C) set to either 15 watts or 30 watts. Liquid flavors available will include tobacco, menthol, dessert, and fruit.

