Procedure. For each session, participants will be asked to refrain from tobacco/nicotine use for ≥ 12 hours and eating food/drinking caffeinated beverages for 1 hour prior to their scheduled session with verification of tobacco/nicotine use status upon arrival at the lab (expired air CO ≤ 7 for ECIG users and ≤ 10 ppm for Dual Users). At the start of the

session, participants rest for 30 minutes, at this time participants will be asked about symptoms experienced since last visit. During this time, participants will not be allowed to use their phones, eat or drink outside beverages but we will provide water to drink and they are invited to read books/magazines or watch movies that we provide to them. Thirty minutes (min) after session onset, participants will sample the session-specific product (2 puffs) followed by a 1 hour rest period, following the same guidelines as the first 30-minute rest period. After the rest period, baseline subjective measures to assess tobacco abstinence symptoms will be completed. Immediately after either the PRT or the DPT/MCP tasks will be completed. The PRT takes approximately 40 minutes to complete and the DPT/MCP takes approximately 40 minutes to complete. Please note that this order, PRT – DPT/MCP or DPT/MCP – PRT, is counterbalanced across participants to control for the effects of completing one task set prior to the other. Following the 1st counterbalanced task assessment, participants will complete a 60-minute rest period. The study procedures should take no more than 240 minutes or 4 hours but study procedures could be completed earlier than that based on decisions the participant makes during the PRT.

0m – CO Check; Physio data collection begins, additional questions about symptoms asked.

30m – 2 puff sample

90m – CO Check; Subjectives measure 1

100m – DPT/MCP OR PRT

140m – Behavioral Measure 1 completed

Subjectives measure 2

Begin 60m rest period

200m – Subjectives measure 3

DPT/MCP OR PRT

240m – Behavioral Measure 2 completed

Subjectives measure 4

end session

Product administration will consist of a 2 sample puff at the beginning of each session. Three behavioral choice tasks will be performed (DPT, MCP, and the PRT). Two of those, (The MCP and the PRT) may yield additional puffs, depending on the decisions made. See the Behavioral Measures section below for more details.

Measures.

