Importantly these tasks are programmed to end early if participants report zero consumption for assessed products. Estimated time per measure is <3 min, and each measure will only be completed once per session.

The Multiple Choice Procedure (MCP) questionnaire consists of three columns and 15 rows. Ten puffs from the session specific product (session specific ECIG or Own Brand ECIG/Cigarette) will be shown in the center column while varying amounts of money (\$0.01 - \$10.24) will be presented in ascending order in right column. Participants will be instructed to circle whether they prefer puffs or money for each of the 15 choices given to them. The MCP will only be administered once, immediately following the DPT. Immediately after the questionnaire is completed, participants will be presented with one of their choices (drawn randomly) and given a 10-minute 'consumption' period in which to take puffs or receive money. After the consumption period, participants will rest for 10 minutes before either ending the session or beginning the 60-minute rest period.

Subjective measures. Repeatedly within each condition we will use the Minnesota Nicotine Withdrawal Scale and the Direct Effects of Nicotine Scale to measure nicotine withdrawal symptoms before and after each behavioral measure.

Data analysis. Subjective, physiological, DPT, MCP, and PRT data will be prepared as reported elsewhere ([name] et al., 2017; Rusted et al., 1998; [name] et al., 2010). Elasticity is estimated using an exponential demand function with nonsystematic DTP data excluded based on two criteria: trend, or whether the participant had a general decrease in consumption from the lowest to highest price; and bounce, or whether a participant reported higher consumption at sequential higher prices (Stein et al., 2015). In general, analysis will involve a mixed (between- and within-subject) ANOVA. Demographic data will be examined to determine if there are significant between-group differences on measures that may be related to study outcomes (some differences are expected, like cigarette use). Unexpected between group differences will be considered as potential covariates in the primary analysis (see Evans et al., 2006). For all ANOVAs, adjustments for sphericity violations and post-hoc testing using Tukey's HSD or planned contrasts with Bonferroni corrections will be used (Keppel, 1991). Missing data will be imputed using multiple imputation techniques (Allison, 2001).

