Tobacco/nicotine abstinence syndrome: As individuals entering this study may exhibit signs of nicotine dependence there is a possibility that during the 12-hour tobacco/nicotine abstinence period prior to each session, participants may experience symptoms associated with tobacco/nicotine abstinence including irritability, anxiety, restlessness, hunger, and difficulty sleeping. Importantly these effects can be uncomfortable but are not medically dangerous. Participants will be informed of these potential abstinence-related side effects during the informed consent.

During the sessions, if the participant reports experiencing small droplets of ECIG liquid during inhalation, we will immediately replace the device he or she is using in the session.

We will inform participants of the other ECIG-related side effects during the informed consent process.

The risk of seizures is minimized by excluding participants with any history of seizures, and by having a full-time RN available, as well as monitoring of vital signs. In addition, some of the reported seizures occurred in users who were using other substances such as marijuana or amphetamines--the risk of seizures in this study is reduced as we are administering nicotine and no other substances.

The risk of respiratory illnesses related to ECIG use is minimized by the limited ECIG use that occurs in each session (10 puffs plus a 60 minute ad lib use period). Participants are informed about recent reports of ECIG-related respiratory

illnesses and are informed that the CDC has advised people to stop vaping. Participants are also advised to monitor themselves for symptoms and to seek medical attention if they have concerns. In addition, we will ask about respiratory and gastrointestinal symptoms at screening and before each session begins. Answers given at the beginning of each session will be compared to the participants' previous answers, and if any symptoms have increased, [name] will be asked to review the symptoms. In some cases, we may contact [name] to determine if a session can proceed.

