1. * Is it likely investigators could discover a participant's previously unknown condition (e.g. disease, suicidal thoughts, wrong paternity, pregnancy, genetic results, or other findings that may be of importance to health or well-being) or if a participant is engaging in illegal or reportable activities:

Yes

No

2. * Describe any possible pertinent or incidental findings stemming from research-only procedures that may be of importance to a subject's health or well-being or which may relate to illegal or reportable activities.

During screening we assess blood pressure.

During screening we assess if female participants are pregnant.

During screening we ask questions about marijuana/cannabis use and other illicit drug use.

During screening and at the beginning of a session we ask about respiratory and gastrointestinal symptoms.

3. * Explain what actions or procedures should research personnel take to handle such a discovery :

If a participant's blood pressure is high, research staff will advise the participant to talk to their own doctor and to get treatment.

If a participant is pregnant, research staff will advise the participant to seek prenatal care.

If a participant reports marijuana/cannabis use, although this is an illegal activity, the search staff will not take any actions. This study does have a certificate of confidentiality, which provides additional protections for participants.

Individuals who engage in illicit drug use in the past month will not be eligible for an in-person screen or to participate in the clinical laboratory portion of the study.

Answers given about respiratory and gastrointestinal symptoms will be compared to the participants' previous answers, and if any symptoms have increased, [name] will be asked to review the symptoms. In some cases, we may contact [name] to determine if a session can proceed.

4. * Will findings be disclosed to participants and/or any other person/group outside of the study team?

Yes

No

5. * Describe a communication plan addressing:

1. What criteria will be used to determine which pertinent and/or incidental findings will be communicated, including the following for health related findings:

- The reliability of the tests/images, such as being done in a CLIA-certified lab,
- Whether the meaning and significance of the findings are known,
- Whether the findings reveal a significant risk of a serious health condition,

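### The only required review of respiratory and gastrointestinal symptoms needs an increase over earlier answers, so a symptom present at screening and stable afterwards never triggers it

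*Protocol*

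**What the plan says.** Protocol, Risks, Discomforts, Potential Harms and Monitoring, question 2, lists symptom questions among the measures against e-cigarette-related respiratory illness: "In addition, we will ask about respiratory and gastrointestinal symptoms at screening and before each session begins". The required action follows: "Answers given at the beginning of each session will be compared to the participants' previous answers, and if any symptoms have increased", a designated person is asked to review them. A further sentence allows a named person to be contacted, in some cases, about whether a session may go ahead.

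Protocol, Pertinent and Incidental Findings, question 2, names the same answers as a possible finding: "During screening and at the beginning of a session we ask about respiratory and gastrointestinal symptoms". Question 3 asks what staff should do about such a finding, and the reply uses the same comparison: "Answers given about respiratory and gastrointestinal symptoms will be compared to the participants' previous answers, and if any symptoms have increased", the symptoms are reviewed. The sentence on contacting a named person is repeated.

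Product use starts at the screening visit. Under Study Procedures, question 7, Recruitment and Enrollment, candidates choose a liquid: "They will be given the opportunity to test four ECIG liquid flavors using the study ECIG device". The SAP does not address these symptom answers.

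**The concern.** A rule that looks for an increase suits the detection of new illness during the study. It does not suit screening, where the text describes no earlier symptom answer to compare with. The protocol nevertheless asks the questions at screening and lists the answers as a possible screening finding.

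The risk section (question 1) names breathing difficulty, breathlessness, cough and chest pain as symptoms seen ahead of hospital admission. A candidate with one of these and no diagnosis could answer truthfully at screening, give the same answer at every session, and never reach the reviewer whom the protocol appoints for this purpose. What is at stake is whether a stated safeguard covers people who have symptoms before they use any study product. No endpoint, analysis or sample size is affected.

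**Working it through.** **The rule applied at each time point.** Let s0 be the symptom answer at screening and s1 to s5 the answers before sessions 1 to 5. A review is required at session k when the answer exceeds previous answers. Take a present and stable symptom: s0 = s1 = ... = s5 > 0.

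| Time point | Earlier answer described | Increase | Required review |
|---|---|---|---|
| Screening | none | cannot be computed | no |
| Sessions 1 to 5 | s0 and any earlier session answers | sk − previous = 0 | no |

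The result is no required review at 1 + 5 = 6 time points. It is the same whether the comparison is with the last answer or with all earlier ones.

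**Comparison with other screening findings.** In Pertinent and Incidental Findings, question 3, the replies on blood pressure, pregnancy and drug use need no earlier value. The communication plan in question 5 covers disclosure to the participant of blood pressure and pregnancy findings only. In the risk section, 140 mmHg systolic or 90 diastolic or above at screening leads to referral and to exclusion or possible withdrawal (questions 2, 4 and 5). A heart rate above 120 beats per minute, or pressure above 150 systolic or 100 diastolic, leads to an alert to the nurse or medical monitor (question 4). Each of these acts on a single reading. The visible text gives no single-answer trigger for symptoms.

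**Exposure without a required review.** Inputs from Study Procedures, question 7:
- Sample puffs: "Product administration will consist of a 2 sample puff at the beginning of each session". There are 4 study-device sessions and 1 own-brand session, so 2 × 4 + 2 × 1 = 10.
- Multiple Choice Procedure: "Ten puffs from the session specific product (session specific ECIG or Own Brand ECIG/Cigarette) will be shown in the center column". One choice is drawn at random and yields puffs or money, so 0 to 10 puffs per session: 0 to 10 × 5 = 0 to 50.
- Sum: 10 + 0 = 10 up to 10 + 50 = 60 puffs.

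Progressive Ratio Task puffs and the testing of up to four liquids at screening come on top. The risk section describes use per session differently, as 10 puffs plus a 60-minute free-use period. That would be 10 × 5 = 50 puffs plus 60 × 5 = 300 minutes. The counts above follow the procedure section.

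**Review load of a screening trigger.** Up to 300 people may be consented (Study Population), so at most 300 screening reviews. The documents give no symptom rate. Purely as an assumption, 5% to 40% reporting any symptom would mean 300 × 0.05 = 15 to 300 × 0.40 = 120 reviews.

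**The case against.** The strongest reply is that the protocol leaves several other ways to stop such a candidate:
- The sentence on contacting a named person carries no explicit condition of an increase. A reader might infer that review after an increase is the only staff action tied to these answers. The documents do not support that: this is a second, discretionary action.
- Eligibility is confirmed from baseline measures at the screening visit, and participants must be healthy by self-report. A symptom answer is itself a self-report.
- The exclusions begin from diagnosed conditions but also reach, through consultation, any medical condition that may affect safety. Withdrawal for any safety concern is allowed, including at baseline.
- Participants already use e-cigarettes regularly and abstain for at least 12 hours before each session. Limited use, warnings and advice to seek care apply to everyone, so the added risk may be modest.
- The baseline forms and the pre-session symptom checklist are listed as uploaded documents and cannot be seen here. Some pages are also missing from the public copy. A screening rule may exist in any of these.

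A reader might also infer that the session question, "participants will be asked about symptoms experienced since last visit", is a second test for change. It is not. It sets a recall window, and a cough that persists from screening falls inside it and would be reported again.

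All of this limits the point, but none of it removes it. Each route is a matter of judgment, and none is linked to the symptom answers. The contact sentence concerns whether a session proceeds and gives no criterion for a stable symptom or for flavor testing. The rule on communication with the medical monitor depends on an adverse event. A rule in an unseen form would answer the point, apart from a missing cross-reference.

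**Conclusion.** The point holds for required review. In the visible text, a respiratory or gastrointestinal symptom first reported at screening and unchanged afterwards triggers no required review before flavor testing or before any of the five sessions. This is a gap in a stated safety rule, because the protocol itself asks the questions at screening and treats the answers as a possible finding.

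It would go too far to conclude that nobody could stop a symptomatic candidate, or that participants face a known extra risk. Discretion exists at several places. The 10 to 60 puffs measure exposure only, and the number of affected candidates is unknown. The conclusion assumes that the unseen forms and pages contain no screening rule for symptoms. It is a cheap improvement, not a fault that undermines the study.

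**What to change.** In question 2 of the risk section and question 3 of Pertinent and Incidental Findings, add one sentence: any respiratory or gastrointestinal symptom reported at screening goes to the same reviewer who sees increases at sessions, before flavor testing and enrollment, and the investigator and medical monitor decide on entry. Keep the increase rule for sessions. If the uploaded baseline form or symptom checklist already contains such a rule, cite it in both places instead.

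The change uses the same questions and the same reviewer. Its cost is some extra reviews, delays at the screening visit and possibly screen failures. The number is unknown, with the ceiling of 300 reviews shown above.

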Communication with between laboratory staff and the PI/Medical Monitor occurs as soon as possible during and/or after any adverse event occurs.

The PI and Medical Monitor are available by mobile phone, office phone, and email. These numbers are posted centrally in the laboratory.

4. CV/Biosketch: (required for PI, Medically/Psychologically Responsible Investigators and Student/Trainee Investigators)

ID: HM20012696

View: SF2 - Conflict of Interest

Conflict of Interest

The PI should ask the questions on this page of all research personnel who are engaged in the research, including subrecipient investigators and personnel.

1. * To the best of your knowledge, do you (as PI) or any other engaged individual have a financial interest related to this study?

Financial interests include utilizing your licensed intellectual property in the study; serving as a paid consultant, or advisory board member, or officer/director with a related entity; and equity or business ownership in a company that is related to this project.

Yes

No

2. * If Yes, provide:
- Name(s) of the engaged individual(s) with a related financial interest
- Brief description of the financial interest Any individual named here should be designated as a 'COI Investigator' on the Personnel page, even if they were not initially designated as a 'COI Investigator', and complete a Financial Interest Report (FIR) in the Activity and Interest Reporting System (AIRS).

[name] is a paid consultant in litigation against the tobacco industry and the electronic cigarette industry.

3. * To the best of your knowledge, do you (as PI) or any other engaged individual have a non-financial interest related to this study?

Non-financial interests could include such things as:
- utilizing your unlicensed intellectual property in the study,
- serving as an unpaid advisory board member or officer/director with a related entity, and
- equity or business ownership in a company that has yet to make a profit and is related to this project
- conflicts of time/effort,
- personal and professional relationships/affiliations,
- intellectual passions or personal beliefs
- other factors that could create bias in the study

Yes

No

4. Describe any institutional conflict of interest that you or any member of the research team are aware of that pertains to this research:

An institutional conflict of interest is a situation in which financial interests of the University or University leadership may affect research activities at VCU.

ID: HM20012696

View: SF2 - Other VCU Requirementsv2

Other VCU Requirements

This page asks questions on behalf of other ancillary offices, committees and departments at VCU regarding institutional requirements that could apply to this research. In some cases, these requirements could also impact the consent process or other aspects of the IRB's review.

Based upon answers provided earlier in this form, certain ancillary sections below may not have questions displayed if those requirements are not applicable to this study.

1. Cost Coverage Analysis

Information on coverage analysis requirements and processes can be found through VCU's Clinical Research Compliance Program at https://research.vcu.edu/compliance_program/research_coverage.htm

1. * VCU requires that all clinical research studies be evaluated to determine if a Coverage Analysis is required. Has your study been evaluated by an institutionally designated Coverage Analysis Specialist?

Yes

No

Not Applicable

2. ClinicalTrials.gov Program & OnCore

For guidance, see <https://ctr.vcu.edu/support/clinical-trials/clinicaltrials.gov.html> or email [contact]

1. * Is this a Clinical Trial?

Yes No

2. * The PI acknowledges awareness of the following requirements for posting clinical trial consent forms:

- Each clinical trial under the 2018 Common Rule that is conducted or supported by a Federal department or agency must post one IRB-approved consent form that was used to enroll subjects on a publicly available Federal website [45 CFR 46.116(h)].

- When engaged in multi-site research, the VCU PI is responsible for confirming with the lead site who is responsible for posting the informed consent form.

- When VCU is the lead site, the VCU PI is responsible for posting the informed consent form (unless the federal department or agency will post it).

Yes No

3. Community Engagement

For more information, see <https://community.vcu.edu/>

1. * Is there a community partner in this research study?

Yes

No

4. Family Educational Rights and Privacy Act (FERPA) Requirements

For guidance, see <https://rar.vcu.edu/records/family-educational-rights-and-privacy-act/>

1. * Does this study involve obtaining information from VCU students' educational records (see help text)?

Yes

No

5. General Data Protection Regulation (GDPR) Requirements

Contact the VCU Research Data Privacy Office with questions about GDPR requirements:

https://research.vcu.edu/data_privacy

1. * Does this study involve the VCU site, or any sites under the VCU IRB's oversight, obtaining data in, or from, the European Economic Area? (see Help Text for list of countries included in the EEA)

Yes

No

6. Information Security

For guidance, see <https://ts.vcu.edu/askit/essential-computing/information-security/>

1. * Using the VCU Data Classification Tool, please determine the appropriate data classification category for the data that will be collected or used in this research.

Note: if the data falls into Category 1, a data security management plan is required by University Information Security Office.

See help text for information on accessing the VCU Data Classification Tool, and for information on creating a data security management plan.

Category 1: all data that require breach notifications in the event of improper release, including all non-publicly available personally identifiable information covered by HIPAA and Commonwealth of Virginia regulations.

Category 2: all proprietary data that if improperly released has the potential to cause harm to the institution, its mission or its reputation that do not require breach notifications.

Category 3: all non-proprietary data that is considered publicly available for unrestricted use and disclosure. Such information is available to all members of the University community and to all individuals and entities external to the University.

2. * I confirm use of the VCU Data Classification Tool in determining the data classification category selected in Question 1:

Yes

No

7. Massey Cancer Center Protocol Review and Monitoring Committee (PRMC)

For guidance, see <https://www.massey.vcu.edu/research/protocol-review/>

1. * Does this study target any of the following populations?

- cancer patients,
- family members of cancer patients,
- cancer healthcare providers, or
- cancer prevention where cancer is integral to the research question

Yes

No

8. VCU Health Department of Patient Centered Services

1. * Does your study involve a satisfaction survey administered to VCUHS patients (*See Help Text):

Yes

No

Not Applicable

9. VCU Faculty-Held IND or IDE

For guidance, see <http://go.vcu.edu/indide>

10. VCU Health System locations

1. * Will research activities occur in patient care areas of the VCU Health System (including at CHOIR, Community Memorial Hospital, VCU Medical Center and Massey Cancer Center)?

Yes

No

11. VCUHS Department of Pathology

Learn more about requesting and establishing an account with Pathology here: See

<https://pathology.vcu.edu/research-services/>

1. * I am aware that I may need to establish a research account with VCUHS Department of Pathology for specimen processing:
- Yes
- No

12. VCU Institutional Biosafety Committee (IBC)

To contact the Biosafety Office, call [contact] or extension [name], or view their website at: <https://research.vcu.edu/ibc>

1. * Does this project involve the use of Bio-Hazardous Substances such as gene transfer, use of organisms or their products, biological toxins, and/or viruses?
- Yes
- No
2. * Does this project involve recombinant DNA (rDNA) and/or synthetic nucleic acids?
- Yes
- No

13. VCU Radiation Safety Committee (RSC)

To contact the Radiation Safety Section, call [contact], or view their website at: <https://research.vcu.edu/rsc>

1. * Does this study involve radiation exposure and/or scans involving radiation (e.g.: PET, MRA, CT, DXA, nuclear medicine, etc.)?
- Yes
- No

14. Virginia-Stem Cell Research Oversight (SCRO)

For guidance, contact the Office of Research Integrity and Ethics (ORIE) at: [contact]

1. * Does this study involve stem cells?
- Yes
- No

15. VCU Scientific Review Committee (SRC)

For guidance, see <https://cctr.vcu.edu/support/study-participation-recruitment/scientific-review>

1. * Has this human subjects protocol (not the grant application) already been reviewed by the funder of a sponsored project (e.g. a federal, state or non-profit funding sponsor)?
- Yes
- No

Based upon your responses, this study will be routed to the VCU Scientific Review Committee (SRC) when it is submitted. After SRC review is completed, the IRB will receive the study.

16. Upload any documents requested in the questions above:

ID: HM20012696

View: SF2 - Institutional Requirements Complete

Institutional Requirements Complete

Protocol Progress:

- ① INITIAL SETUP
- ② BACKGROUND, RATIONALE & GOALS
- ③ RESEARCH PLAN
- ④ CONSENT PLAN
- ⑤ RISKS, PRIVACY & CONFIDENTIALITY
- ⑥ POPULATIONS WITH SPECIAL CONSIDERATIONS
- ⑦ INSTITUTIONAL REQUIREMENTS
- ⑧ DOCUMENTS

Click Continue below to go to the next section

Documents

1. Upload any documents that the VCU IRB will need to conduct a review of this submission:
A list of potential documents is given in the help text.

NOTE: The delete function should only be used if an incorrect document is uploaded or added to the system AND that document has not been reviewed and approved by the IRB. Do NOT delete documents that the IRB previously reviewed and approved.

Once you have uploaded a document to RAMS-IRB, any changes to that document (i.e. different versions of the same document) should be added to the IRB submission by using the Update button. To provide updated documents, follow these steps:

- Click the Update button located to the left of the document to be updated.
- In the Add Document window, click the Choose File or Browse button, select the file you are adding, and click on the Open button.
- Click OK to close the Add Document window, and the system will upload the revised document. RAMS-IRB will automatically provide a version number for the document.

To access previous versions of a document in RAMS-IRB you must use the History link associated with the document.

- Click the View or Update button located to the left of the document you wish to access.
- In the Add/View Document window, click the "History" hyperlink located to the right of the file name.
- A separate window will open that shows all versions of the document that have been added to RAMS-IRB. Click on any file name to download and view the document.

	Document Name	Document	Version	Date Modified	Uploaded By	Type	Approved
View	Informed Consent Form	HM20012696 Informed Consent_02.07.2020_CLEAN.pdf	0.38	4/6/2020 7:08 AM	[name]	Consent/Assent/Information Sheet	Yes
View	CSTP Vaper Advertisements PDF	WATT_CSTP_Vaper_Combined_02.07.2020_CLEAN.pdf	0.08	2/7/2020 3:43 PM	[name]	Recruitment/Advertising	Yes
View	CSTP Dual Advertisements PDF	WATT_CSTP_Dual_combined_02.07.2020_CLEAN.pdf	0.03	2/7/2020 3:40 PM	[name]	Recruitment/Advertising	Yes
View	Baseline Self Report Physio Measures	U54_Baseline forms All_12.18.2019_CLEAN.docx	0.19	12/19/2019 2:23 PM	[name]	Research Measure	Yes
View	Pre-session Symptom Questions	WATT Pre-session symptom Checklist-12.18.2019_CLEAN.docx	0.03	12/19/2019 2:22 PM	[name]	Research Measure	Yes
View	Text, Email, Call Scripts	U54_Text, Email, Call, Scripts_11.18.2019_CLEAN.docx	0.11	11/25/2019 3:14 PM	[name]	Other	Yes
